#### **Data Collection Center**

The Kansas City Heart Rhythm Research Foundation will be the coordinating site for the study. A project manager (PM) with the help of the PI will create the study worksheets and create the CRFs. The sites will complete the paper CRF and submit via secure email to the project manager. The PM will assist the Database Manager (DM) with updating the access database and providing computer support for outside centers. All data will be submitted via secure email including de-identified patient data that is to be used as source.

Participant's data will be de-identified and a code will be assigned. The code will consist of Site Number, Patient Number and Patient Initials. The coordinator at that site will have access to the code; the linking list will be destroyed at the completion of the project.

**Statistical analysis:** Patients will be randomized in a stratified manner to control arm versus treatment arm. We will analyze the differences in secondary endpoints between the two groups for major, minor bleeding and cardiovascular mortality up to 30 days post ablation. Categorical variables will be reported as counts and percentages and continuous variables will be expressed as mean  $\pm$  SD. Continuous variables will be compared using t-test for normally distributed data or Mann Whitney U test for non-normally distributed data as deemed appropriate. Categorical events will be compared using chi-square test for parametric data.

Univariate and multi-variate analysis will be performed to identify the predictors of systemic thromboembolic events and mortality. This is a pilot study to study the feasibility and safety of the study. A larger study will be done in the future if there is a positive signal.

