Use of oral anticoagulation after left ventricular arrhythmia ablation is not standard of care at this point and is anecdotally used in high risk patients with LV aneurysms and those with severe LV dysfunction. Even when used post ablation anticoagulation with warfarin is fraught with several practical issues including the time to therapeutic range and the need for bridging with unfractionated or low molecular weight heparin with implications to prolonged length of stay and increased bleeding complications. So, the novel non VKA agents probably are a better fit for this specific situation. Early experience with all four currently available agents (Dabigatran, Rivaroxaban , Apixiban and Edoxaban) for periprocedural anticoagulation seems to be safe and efficacious. DOAC is a direct oral inhibitor of Prothrombin/factor Xa inhibitor and thereby mediates its anticoagulation effect . In the recently published double blind randomized clinical trial DOAC was found to be superior to warfarin in decreasing the risk of stroke and also had fewer complications of bleeding and death in patients with atrial fibrillation/flutter .

We believe that peri-procedural DOAC use for left ventricular arrhythmia ablation will provide effective anticoagulation without increasing bleeding complications and may decrease the incidence of both symptomatic and asymptomatic cerebrovascular events, TIAs and strokes.

Magnetic resonance imaging (MRI) is the most commonly used imaging test to detect acute ischemic stroke and asymptomatic CVEs. There is a natural apprehension about the use of MRI scanning in patient with Cardiac Implantable Electrical Devices (CIEDs) . However, there are protocols in place showing MRI examination of patients with CIEDs with minimal or no side

effects . There is increasing data on the safety of the use of MRI in CIED patients which perhaps led to the participating institutions routine use of MRI in defining ventricular scar prior to RF ablation to optimize the treatment strategy and outcomes. The potential for adverse effects on the CIED during MRI of the head is far lower than imaging the chest as the device will not be in the direct MRI field as it is with head scanning. When performed with appropriate monitoring the post left ventricular arrhythmia ablation MRI scanning of the brain can be safe and help us examine an important issue that has not been well defined.

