## **INVESTIGATIONAL PLAN**

### **Study Design and Duration**

This is a multicenter, randomized, prospective study to determine, if DOAC can be used periprocedural in patients undergoing a scar left ventricular arrhythmia ablation. Patients will be screened from both the clinic setting and upcoming EP lab schedule. The patient's chart will be reviewed and those that meet inclusion/exclusion will be approached for the study. For this study, we intend to enroll 52 consecutive subjects who are undergoing a scar left ventricular arrhythmia ablation at participating institutions if they meet all other inclusion criteria and do not have any exclusion criteria. Patients will be randomized in a 1:1 fashion.

Figure 1 shows the use of ASA or DOAC for left ventricular arrhythmia ablation.

[figure not shown]
Patients undergoing left ventricular arrhythmia ablation will be consented and randomized to either ASA 81 mg or 100 mg daily or DOAC twice daily. Patients randomized to ASA will continue or start ASA 81 mg or 100 mg by mouth daily, and continue up to 30 days after the procedure. Patients randomized to DOAC group will stop the ASA if they are currently taking it; DOAC 5 twice daily will be started 3 hours after hemostasis and continue for 30 days post procedure.

The drugs to which they are assigned to will be continued at least for 30 days post left ventricular arrhythmia ablation. All subjects will be followed from baseline to 30 days post procedure. At this time they will have completed the study and can stop either DOAC and/or Aspirin at the physician's discretion.

*Final revised protocol*

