### **DATA MONITORING COMMITTEE**

To meet the study's ethical responsibility to its subjects, an independent data safety monitoring Board (DSMB) will monitor results during the study. The board consists of 2 physicians and 1 statistician who have no formal involvement or conflict of interest with the subjects or the investigators. Records will be reviewed after the first 50 patients and then at the completion of the study.

If the major bleeding events in the DOAC group occur at >15% but <30% (absolute event rate) of those in the ASA group during any of the assessments, a recommendation will be made to consider modifying the study by the members of the DSMB. First consideration to modify is to decrease the dose of the drug to 2.5mg PO twice daily. If the major bleeding events in the DOAC group occur at >30% (absolute event rate) of those in the ASA group during any of the assessments, a recommendation will be made to stop the study by the members of the DSMB.

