### **STATISTICAL CONSIDERATIONS**

#### ***Study Management and Sample Size Justification***

This is a pilot study and 52 total patients will be enrolled in the study. We expect to analyze a total of 50 patients and each arm will consist of 25 patients. The additional 2 allows for attrition. Since this is a pilot study, the number needed to treat to achieve a pre-specified statistical significance cannot be calculated accurately. Exact sample size could not be given due to lack of pre-existing data on this subject. We hypothesize a 30% difference in outcomes can be seen with a total sample size of 50 patients.

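### Bleeding is compared by a chi-square test with 25 patients per arm and no interval, so a non-significant result cannot support a claim that DOAC does not increase bleeding

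*Combined protocol and SAP*

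**What the plan says.** The background (Overall Risk/Benefit Assessment) states the belief that peri-procedural DOAC "will provide effective anticoagulation without increasing bleeding complications". Both bleeding items under Secondary Objectives are worded as estimation of the effect of DOAC against aspirin, one for major and one for minor bleeding.

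The Statistical analysis paragraph, printed under Data Collection Center, then says: "We will analyze the differences in secondary endpoints between the two groups for major, minor bleeding and cardiovascular mortality up to 30 days post ablation". It provides counts and percentages by arm and a chi-square test for categorical events. It names no interval for a difference, significance level, sidedness or continuity correction. It describes the purpose thus: "This is a pilot study to study the feasibility and safety of the study". It foresees a larger study after a positive signal, which it does not define.

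On size, the sample size section says: "We expect to analyze a total of 50 patients and each arm will consist of 25 patients".

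The Data Monitoring Committee section adds a separate rule on observed major bleeding, reviewed after the first 50 patients and at completion. Its first trigger begins "If the major bleeding events in the DOAC group occur at >15% but <30% (absolute event rate) of those in the ASA group".

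**The concern.** The objective is to estimate an effect and the background belief is one of no increase, but the planned inference is a test that can only show a difference. When such a test is non-significant, it does not say which excesses remain compatible with the data. With 25 per arm and few expected bleeds, that range is wide.

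Bleeding is the main harm to be weighed against any benefit of the tested strategy, and the pilot is meant to inform a larger trial. If its report gives two percentages and a p-value above 0.05, the designers of that trial cannot tell whether a large excess has been excluded or merely not detected.

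**Working it through.** **Inputs.** From the documents: 25 analysed per arm, 1:1 allocation, chi-square test. Not in the documents, so assumed: two-sided 0.05, and major bleeding of 0% to 5% on aspirin.

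**1. The plan's own size statement.** The sample size section says: "We hypothesize a 30% difference in outcomes can be seen with a total sample size of 50 patients". It does not give the endpoint, scale, control rate, significance level or power, so the 50 cannot be reproduced. As an illustration, take an absolute 30-point difference, two-sided 0.05 and 80% power:

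n per arm = [1.96·√(2·p̄(1−p̄)) + 0.842·√(p₁(1−p₁) + p₂(1−p₂))]² / (p₂−p₁)²

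For 0% v 30%, p̄ = 0.15 and n = (0.990 + 0.386)²/0.09 = 21.0, so 22. The same formula gives 24 for 2% v 32%, 27 for 5% v 35% and 32 for 10% v 40%. On this reading, 25 per arm suits a 30-point difference only when the lower rate is near zero. It is not sized for a smaller bleeding excess.

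**2. How often the test misses a true excess.** The miss rate is 1 − P(p ≤ 0.05 with more bleeds on DOAC), summed exactly over all 26 × 26 tables with binomial probabilities.

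The 0% aspirin case can be checked by hand. Against 0/25, 3 DOAC bleeds give p = 0.074 and 4 give p = 0.037, so at least 4 are needed. For a true 15-point excess the miss rate is P(Bin(25, 0.15) ≤ 3) = 0.471. With continuity correction, 5 bleeds give p = 0.059 and 6 give p = 0.030, so the miss rate is P(Bin(25, 0.15) ≤ 5) = 0.838.

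| True excess | Aspirin rate | Missed, uncorrected | Missed, corrected |
|---|---|---|---|
| 10 points | 0% | 76% | 97% |
| 10 points | 5% | 79% | 94% |
| 15 points | 0% | 47% | 84% |
| 15 points | 2% | 54% | 84% |
| 15 points | 5% | 62% | 84% |
| 20 points | 0% | 23% | 62% |
| 20 points | 5% | 44% | 69% |

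With a one-sided 0.05 test, the uncorrected misses at 15 points fall to 25% (aspirin 0%) and 48% (aspirin 5%).

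**3. One possible result.** Take 5/25 on DOAC and 1/25 on aspirin. Uncorrected, χ² = 50·(5·24 − 1·20)²/(25·25·6·44) = 3.03, p = 0.082. Corrected, χ² = 50·(100 − 25)²/(25·25·6·44) = 1.70, p = 0.19. The observed excess is 16 points and the test is not significant.

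**4. What an interval would show.** Newcombe's 95% interval combines the Wilson limits (l, u) of the two arms:

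lower = d − √[(p_D − l_D)² + (u_A − p_A)²]; upper = d + √[(u_D − p_D)² + (p_A − l_A)²]

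For 5 v 1 the Wilson limits are 8.9% to 39.1% and 0.7% to 19.5%, with d = 16 points:

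- lower = 16 − √(11.14² + 15.54²) = −3.1
- upper = 16 + √(19.13² + 3.29²) = +35.4

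| Bleeds, DOAC v aspirin | Difference | 95% interval (points) |
|---|---|---|
| 0 v 0 | 0 | −13.3 to +13.3 |
| 1 v 1 | 0 | −15.9 to +15.9 |
| 1 v 0 | +4 | −9.7 to +19.5 |
| 5 v 1 | +16 | −3.1 to +35.4 |

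Even with no bleeds in either arm, an excess of up to 13.3 points stays inside the interval.

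**The case against.** The strongest reply is that this is a pilot. It says that significance-based sizing was not possible, its formal hypothesis concerns cerebrovascular events only, and the no-increase statement is a background belief. All of that is true, and no larger sample is asked for here. The pilot label does not explain why an estimation objective gets a test and no interval.

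Several stronger readings are tempting, and the documents do not support them.

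- **That chi-square is the only check on bleeding.** The DSMB compares observed major bleeding with no significance test, and counts and percentages are reported by arm. If the first trigger means an absolute excess over 15 points, 5 v 1 would trip it whatever the p-value. The protection is limited: it covers major bleeding only, its first look comes after 50 of 52 patients, and it guides trial conduct rather than the reported conclusion. On that reading, with 25 per arm, it trips about 53% of the time when the true excess is 15 points.
- **That a non-significant result would be declared safe.** No such rule is written. The plan simply does not say how bleeding safety will be concluded.
- **That 15 points is the plan's own threshold.** The trigger mixes absolute and relative wording, so the 15-point reading is an assumption. The gap does not depend on it, as the 10-point figures show.
- **That non-significance is to be expected even under large harm.** With the uncorrected test, a 20-point excess is missed 23% to 44% of the time, so a significant result is then the likelier one.

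**Conclusion.** The concern holds in a limited form. The plan sets out to estimate the bleeding effect but gives only a test of difference, and apart from the DSMB's check of observed major bleeding nothing shows how much excess the data can exclude. Under the assumed two-sided 0.05 and aspirin rates of 0% to 5%, the uncorrected test misses a 15-point excess 47% to 62% of the time and a 10-point excess 76% to 79%; with continuity correction, about 84% and 94% to 97%. A non-significant result therefore cannot support the background's no-increase statement. One-sided testing would reduce the misses at 15 points to 25% to 48%, but the plan does not specify it. This is worth correcting before analysis. It is a gap in analysis and reporting, and it does not show that the trial would claim safety wrongly.

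**What to change.** In the Statistical analysis paragraph, add two sentences to this effect:

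*For major and, separately, for minor bleeding up to 30 days, the main summary will be the DOAC minus aspirin risk difference with a two-sided 95% Newcombe interval, reported with the counts in each arm. A non-significant difference will not be taken as evidence that DOAC does not increase bleeding.*

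The chi-square result may stay as a supplementary figure.

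Do not add a 15-point acceptance margin. The DSMB section treats its trigger as a reason to consider modifying the study and nowhere says that a smaller excess is acceptable. That choice is a clinical judgement the documents do not make, and the trigger does not cover minor bleeding. The ambiguous wording of the trigger should be reconciled separately by the sponsor.

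The cost is two sentences and one interval per bleeding endpoint, with no extra patients or data. The small downside is that the pilot may have to report bleeding safety as inconclusive.

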### **Overall Risk/Benefit Assessment**

Atrial fibrillation (AF) is associated with 5 times increased risk of cerebrovascular events compared to patients in Sinus rhythm [2]. Even in patients undergoing Radiofrequency Ablation (RFA) for atrial fibrillation, the incidence of symptomatic cerebrovascular events (CVE) was 2.3% and 41% of those are from transient ischemic attacks and 25% are from ischemic CVEs, despite being on anticoagulation. The incidence of asymptomatic CVEs rises to 14% after the ablation for AF, detected by Flair enhancement MRI. Multiple trials have shown that the asymptomatic CVEs and/or micro infarcts can increase the odds of having dementia. The incidence of stroke immediately after ablation for left ventricular arrhythmias has ranged from 0 to 2.7% to 7.5% depending on the case series, but there aren't many studies to quantify this problem clearly. Interestingly, the amount of tissue ablated in the ventricles is not any smaller than what is done in the left atrium. Even though the stunning phenomenon that is seen with the left atrial appendage may not be relevant to the ventricular tachycardia ablation, the extensive endothelial denudation and subclinical thrombus formation at the sites of ablation is clearly under appreciated. No active strategies to prevent post ablation systemic thromboembolization are available in patients undergoing left ventricular arrhythmia ablation especially on the left side. Similar to AF, the projected incidence of asymptomatic CVEs may be much higher than the incidence of symptomatic CVEs given the multiple reasons like heat generated from the

ablation, possibility of necrosis of myocardium from ablation and manipulation of the left side of the heart, but currently there are no studies that have focused on the incidence of asymptomatic CVEs. It has been therefore recommended to perform cardioversion or ablation only at therapeutic levels of anticoagulation to decrease the risk of thromboembolism and stroke. So far, there are no trials evaluating the efficacy of unfractionated heparin or newer direct thrombin or factor Xa inhibitors in preventing or reducing symptomatic and also asymptomatic CVEs post-left ventricular arrhythmia ablation. Given the high incidence of symptomatic CVEs and possibility of higher incidence of asymptomatic CVEs which has many prognostic implications, this issue warrants further studies.

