### **Study Rationale**

Ventricular tachycardia (VT) is a complex arrhythmia with high mortality rate. ICDs have shown improvement in survival when placed for primary or secondary prevention in such patients, but they are not a cure for VT and they don't prevent recurrences. In addition, painful ICD shocks, not only impair quality of life and psychological health , but they are also associated with increased all-cause mortality. Antiarrhythmic therapy, even though moderately effective, with time and progressive remodeling recurrent VT and subsequent ICD therapies are common. Radiofrequency catheter ablation has emerged as an important therapeutic option to prevent VT recurrences and reduce the frequency of ICD shocks . Catheter ablation provides potential curative treatment in 77-95% of post MI patients presenting with monomorphic VT and around 60% in patients with VT arising from non-ischemic cardiomyopathy . With advancement in technology and newer saline irrigation catheters, the risks are very minimal, with high success rates . In a nationwide sample of 4653 patients who underwent ablation in the United States between 2002 and 2011 for post-myocardial infarction VT, the overall in-hospital complication rate was 11 percent with in-hospital mortality of 1.6 percent . The number of catheter ablations that are being performed for left ventricular arrhythmias continues to grow and varies from region to region and hard to quantify . Both retrograde transaortic approach and trans-septal approach are possible routes for endocardial radiofrequency ablation (RFA) with embolic risk associated with thrombus formation on the ablation catheters and sheaths, micro thrombus

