#### **STUDY END POINTS:**

##### **Primary Objectives**

Primary end point: To estimate the new symptomatic (Stroke and TIA) and asymptomatic CVEs (brain MRI lesions) and systemic thromboembolism in patients undergoing left ventricular arrhythmia ablation with a novel oral anticoagulant ( DOAC) when compared to aspirin only.

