##### **Secondary Objectives:**

- To estimate the impact of DOAC on major peri-procedural bleeding in patients undergoing left ventricular arrhythmia ablation when compared to ASA. Assessment done up to 30 days post procedure.
- To estimate the impact of DOAC on minor peri-procedural bleeding in patients undergoing left ventricular arrhythmia ablation when compared to ASA. Assessments completed at 1 week post procedure and up to 30 days post procedure.

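### The plan sets out to estimate outcomes against aspirin but names no between-arm effect measure or interval for categorical endpoints, and it commits to multivariable predictor models that about 0.8 expected deaths and at most 3.75 expected symptomatic strokes cannot support

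*Combined protocol and SAP*

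**What the plan says.** The Primary Objectives section aims "To estimate the new symptomatic (Stroke and TIA) and asymptomatic CVEs (brain MRI lesions) and systemic thromboembolism" with the anticoagulant compared with aspirin. The first item under Secondary Objectives is "To estimate the impact of DOAC on major peri-procedural bleeding in patients undergoing left ventricular arrhythmia ablation when compared to ASA".

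The analysis methods are in the statistical analysis paragraph, printed under Data Collection Center. Categorical variables are to be summarised by number and percentage. The only comparative method named for them is "Categorical events will be compared using chi-square test for parametric data". No between-arm effect measure and no confidence interval appears anywhere in the document.

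The paragraph then states: "Univariate and multi-variate analysis will be performed to identify the predictors of systemic thromboembolic events and mortality". It gives no model, covariate list, limit on terms, minimum event count or method for sparse data. It ends: "A larger study will be done in the future if there is a positive signal".

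The sample size section plans to enrol 52 patients and analyse 50, 25 per arm. It hypothesises a 30% difference without saying whether this is absolute or relative.

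**The concern.** There are two separate issues.

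First, an aim of estimation calls for an estimate and its precision. A chi-square p-value gives neither. The decision about a larger study turns on a signal that the plan does not define. At 25 per arm, what matters for that decision is the range of effects still compatible with the data. The method for that range should be fixed before the data are seen, because at these event counts different methods can point in different directions.

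Second, a multivariable model needs events. With about one death, or a handful of strokes, the coefficients are often infinite or arbitrary. Any predictors reported would have no support behind them, yet they would appear as a planned result.

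**Working it through.** **Inputs**
- Analysed patients: 50, 25 per arm (sample size section). The planned 52 reproduces as 50 + 2 for attrition. The 50 itself cannot be reproduced, because no alpha, power or control rate is stated.
- Mortality: "in-hospital mortality of 1.6 percent" (Study Rationale), an in-hospital figure from patients with ventricular tachycardia after infarction, used here as a proxy for 30-day deaths.
- Symptomatic stroke after left ventricular ablation: "has ranged from 0 to 2.7% to 7.5% depending on the case series" (Overall Risk/Benefit Assessment).
- MRI lesions: "The incidence of asymptomatic CVEs rises to 14% after the ablation for AF" (same section). This is a borrowed rate; the section says that no study has addressed these lesions after left ventricular ablation.

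**Expected events = 50 × rate, both arms at the same rate**
- Deaths: 50 × 0.016 = 0.8. P(none) = 0.984^50 = 0.446. P(at most one) = 0.809.
- Symptomatic strokes: 50 × 0.027 = 1.35; 50 × 0.075 = 3.75; the low end is 0.
- MRI lesions: 50 × 0.14 = 7. Adding 7.5% stroke with no overlap: 50 × 0.215 = 10.75.
- If the 30% difference is absolute, total events = 25 × (p1 + p2): 30% v 0% gives 7.5, 40% v 10% gives 12.5, 65% v 35% gives 25.

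**Can a model be fitted?** I assume logistic regression, since no model is named. With treatment as the only term, there is no finite estimate if either arm has no events (or all events). Ignoring the negligible all-events case, the probability is 1 − (1 − (1 − p)^25)².

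| Rate | (1 − p)^25 | No finite fit, treatment alone | No finite fit, five terms |
|---|---|---|---|
| 1.6% | 0.668 | 89% | 96% |
| 2.7% | 0.504 | 75% | 91% |
| 7.5% | 0.142 | 26% | 54% |
| 14% | 0.023 | 5% | 18% |
| 22% | 0.002 | 0.4% | 4% |

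The last column is a simulation (3,000 replicates per rate) with treatment plus four covariates unrelated to outcome. The choice of four is an assumption.

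**How many terms?** As an assumed rule of thumb, allow 5 to 10 events per term.
- 0.8 deaths: 0.08 to 0.16 terms.
- 3.75 strokes: 0.4 to 0.75 terms.
- 7 to 10.75 events: between 0.7 (7 events at 10 per term) and 2.15 (10.75 events at 5 per term).
- 25 events: 2.5 to 5 terms.

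**What the interval adds.** The Newcombe limits for a difference d = p1 − p2 combine the Wilson limits (l, u) of each arm: d − √[(p1 − l1)² + (u2 − p2)²] and d + √[(u1 − p1)² + (p2 − l2)²].
- 4/25 v 1/25: Wilson limits 6.4% to 34.7% and 0.7% to 19.5%. The difference is 12 points, with limits 0.12 − √(0.096² + 0.155²) = −0.063 and 0.12 + √(0.187² + 0.033²) = 0.309. The 95% interval is −6.3 to +30.9 points; chi-square p = 0.16.
- 4/25 v 0/25: 16 points, −0.4 to +34.7. Uncorrected chi-square gives p = 0.037; Fisher's exact test gives p = 0.11.
- 0/25 v 0/25: chi-square cannot be computed; the interval is −13.3 to +13.3 points. The exact upper limit for one arm is 1 − 0.025^(1/25) = 13.7%.

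**Sparse cells.** With equal arms, the expected event count per arm is half the total: 0.4 for deaths, at most 1.9 for strokes, 3.5 to 5.4 with MRI lesions. It is below 5 whenever total events are below 10.

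**The case against.** The first issue is a reporting omission. The plan will give numbers per arm and also promises to analyse between-group differences in secondary endpoints, so the crude difference is one subtraction away and an interval follows from four counts. This stands. A reader might infer that the plan leaves the treatment effect unobtainable, and the documents do not support that.

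A reader might also infer that no thromboembolic model is possible, or that 11 events is a ceiling. Neither is supported. The Study Rationale speaks of thromboembolisation as measured by both symptomatic and asymptomatic events, so MRI lesions may count. The 14% comes from a different procedure, and the protocol itself expects silent lesions to be possibly far commoner than symptomatic ones. With few terms, a model on that outcome would usually converge. The five-term results also depend on covariates the plan never lists.

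The study calls itself a pilot for feasibility and safety, and nothing says that predictors will shape the larger trial. That limits the harm. It does not help the mortality model: doubling the rate still gives only 1.6 deaths. For symptomatic events, TIA and other emboli could add to the strokes. If they doubled the top rate to 15% (an assumption), 7.5 events would support 0.75 to 1.5 terms, still short of a multivariable model.

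Finally, the uncorrected chi-square is not badly sized here. With equal arms at 14%, it rejects in 5.4% of trials by exact enumeration, against 1.7% for Fisher. The case for an exact test is sparse-cell validity, not a large excess of false positives.

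**Conclusion.** Both parts hold, with different weight. The missing effect measure and interval is a modest gap, worth closing because the objectives are worded as estimation and because methods can disagree, as 4/25 v 0/25 shows. The multivariable model is untenable for mortality and for symptomatic thromboembolic events at the rates the protocol quotes: even treatment alone has no finite fit in 89% of trials at 1.6% and 26% at 7.5%.

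If MRI lesions count, the conclusion is weaker. The event number is unknown, and the data would support only a very few terms. Outright deletion of that model is not shown to be necessary.

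The counts assume 50 analysed patients, equal rates in both arms (an effective treatment would lower them), an in-hospital mortality proxy, stroke rates that leave out TIA and other emboli, and no overlap between stroke and MRI lesions at the upper figure. The change should be made before analysis; it does not touch design, sample size or conduct.

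**What to change.** 1. Report the primary composite and each binary secondary endpoint as a risk difference with a Newcombe 95% confidence interval, and name that interval the main result. For stroke and death, also give the count per arm with an exact interval. Replace chi-square with Fisher's exact test where any expected cell is below 5.
2. Delete the multivariable models for mortality and for symptomatic thromboembolic events, and list those events descriptively. State whether the thromboembolic outcome includes MRI lesions. If it does, restrict any model to one or two prespecified terms, or use penalised likelihood, and label it exploratory.

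Cost: wording, minor programming and the loss of the deleted model output. The interval is conservative at low rates: exact coverage is 99.8% at a 7.5% control rate with an odds ratio of 0.2, and 95.5% at equal rates of 14%. Fisher's test is also conservative: if it were used throughout at 40% v 10%, it would reject in 59% of trials, against 73% for chi-square. With the interval leading, this matters less.
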